Power/Sample Size. Aim 1 seeks to address the development of CUD (dependent on the number of symptoms reported) in the MM compared with the WLC group. To assess this, we will use the DSM-5 criteria for CUD, which combines the DSM-IV categories of abuse and dependence into a single disorder measured on a continuum from mild to severe. We have based power sample size requirements on the between and within subject ANOVA of the dependent variable of CUD symptoms, comparing the MM versus WLC conditions tested across the baseline to 3 month periods, where the primary effect of interest is the condition X time interaction. A power analysis using the Gpower computer program²⁹ indicated that a sample of 80 participants per group would be needed to detect small to medium effect (Cohen's $d=.3$) with 90% power using a t test with alpha at .05.

Data Analysis Plan: In general, 3 analytic approaches will be employed, corresponding to three types of comparisons and data:

(a) Numeric Data Assessed at Baseline, 3 Months, 6 Months and 1 year. Measures of addiction, tolerance, and cognitive performance will be analyzed with a between- and within-subject analysis of covariance, the primary between-subject factor being Condition, i.e., the active MM vs. WLC group, and the within-subject factor being time, i.e., assessments at baseline and 3 months. Relevant subject-level numeric covariates (i.e. THC metabolite levels) and categorical factors (e.g. disease category) crossed with condition and possibly interacting with time will be included in the analysis. Covariates such as baseline MJ use, primary disorder for which MM is sought, age, and gender will be of interest. The term of primary interest will be the interaction of condition x time as a test of the hypothesis that assignment to the MM condition will be associated with an increased rate of CUD. A limited amount of backward elimination of nonsignificant ancillary terms will be employed to increase power for effects of more interest (e.g. non-significant terms can be dropped from the models). An additional, analogous repeated-measure ANCOVA, restricted to the MM group, will include the third

assessment at 6 months. The Greenhouse-Geisser adjustment for correlated error will be employed for significance tests with more than one degree of freedom. For all models, residuals will be checked graphically for adherence to assumptions of normality and homoscedasticity, and data transformations applied if needed.

(b) Daily Numeric Data Collected via Dosing Diaries in the First 3 Months. Daily-recorded numeric measures such as dose and frequency of use of MJ, of analgesic, anxiolytic, and/or antidepressant medications, and ratings of pain, sleep, mood, and anxiety will be analyzed as dependent variables in separate analyses. Preliminary exploratory graphical analyses will be conducted using longitudinal “spaghetti plots” in order to check any need for curvilinear models, explore any clusters of trajectories, and address distribution problems such as floors/ceilings, non-normality, outliers, etc. Analysis methods employed will be mixed fixed and random effects longitudinal models. Fixed terms will be Condition (MM vs. WLC groups) and various relevant crossed factors and numeric covariates. Correlated random terms will be subjects’ intercepts and linear rate of change of their trajectories on the dependent variable across days (curvilinear terms will be included if warranted). In order to test the predictive relation of some of the time-varying variables (e.g., frequency of MJ use) on others (e.g., pain recordings or use of analgesic, anxiolytic, and/or antidepressant medications), the former will be included as additional time-varying predictors in models otherwise analogous to those above. Exploratory structural equation models (SEM) and cross correlations of time series will be examined for evidence of underlying causal dynamics. Cross-lagged partial correlations can be used to test direction of effects.

(c) Imaging Data. Imaging data will be analyzed using standard analysis platforms for longitudinal analysis (e.g. FSL and SPM). We will use a linear mixed-effects model approach, with a univariate two-stage specification. The advantage of this method is that it offers flexibility in handling unbalanced repeated measurements with missing data, which is one of the biggest challenges to longitudinal fMRI datasets. At the subject-level, a unique trajectory for each individual is defined for each region or voxel being considered, meaning that activation measurements are condensed into summary statistics for each scan. At the second, population-level, individuals are considered as arising from a population of all such individuals, each with a unique intercept and slope, and a linear mixed-effects model is fit. With this modeling approach, it is reasonable to deduce that the within-individual variances are the fluctuations around the individual-specific trajectory, and the among-individual variances can be described as differences of parameters characterizing these trajectories. As one way to conduct this model using brain-imaging data, statistical measures of brain activity responses serve as the dependent variable and one linear mixed-effect model is then fit for each ROI or voxel. Repeatability of fMRI can be directly addressed via certain parameters of this model.

Risks and Discomforts

Psychosocial risks

Risks: There are no legal risks to the participants associated this study, because medical marijuana is legal in Massachusetts. There is a small social risk associated with participation in this study, as some people may be embarrassed if others found out that they are using medical marijuana.

Minimization: All data will be completely deidentified and anonymized. Please see ‘confidentiality and loss of privacy’ below.

The Co-Investigators on this project include a psychiatrist ([name]) and a clinically-trained clinical psychologist ([name]). If there are any concerns about a subject who is actively suicidal and in need of clinical attention, the PI will be made aware of the issue immediately and will consult with appropriate medical personnel (co-investigators [name] and [name]) to determine appropriate steps. The PI and medically trained co-investigators will assess the needs of the subject and offer the subject either prompt treatment or medical referral, whichever is appropriate

for the situation. There is a licensed clinician on site 40 hours per week, and other MGH resources can be used as necessary.

Confidentiality and Loss of Privacy

Risks: The risk of loss of privacy is judged to be minimal. Online dosing diaries will be collected using Secure Survey, which secures not only the data transmission, but also the storage using industry standard security techniques.

Minimization: Confidentiality will be maintained by numerically coding all data and by keeping all data in password protected databases. Subject information will be accessible only to research staff.

Information about study participants will not leave our institution in any form that would identify individual subjects.

Secure Survey implements multiple layers of security using industry standard techniques:

- SSL Certificates from Trusted Certificate Authorities encrypts all traffic between the user's device and the server
- All database data is encrypted using 256-bit encryption ensuring no data is at risk should the servers be breached
- Browser tokens further secure the flow between pages and help prevent XSS attacks

fMRI Risks

Risks: fMRI is a minimal risk procedure. Although fMRI scanning itself is painless, subjects may experience discomfort. Some may become claustrophobic inside the magnet. Subjects may also be bothered by the beeping and hammering sounds made when the scanner is collecting measurements, and/or experience peripheral stimulation, manifested as a gentle tap or sensation of mild electric shock. Because of the high magnetic field of the fMRI scanner, individuals with pacemakers, cosmetics, or certain metallic implants in their bodies must be excluded. Each potential subject must identify these and other possible contraindications prior to fMRI scanning. Because the scanner attracts certain metals, precautions must be taken to remove metallic objects from the MRI room.

Minimization: Since some subjects may be uncomfortable in the MRI, all subjects will be able to converse with the experimenter via a microphone and speaker system, and will be able to communicate an immediate need to come out or stop the scan via a "panic squeezeball". All efforts will be made to make the subjects as comfortable as possible while in the scanner. A member of the study staff will explain the procedure thoroughly to the subjects prior to scanning, allowing for maximal understanding and comfort. The MRI can be stopped at any time at the subjects' request. In addition, the scanners are equipped with an emergency button that the subject can press if necessary. A qualified M.D. will always be on site or reachable by pager in the unlikely event that an adverse event occurs. If there are any concerns about a subject in need of clinical attention, the PI will be made aware of the issue immediately and will consult with appropriate medical personnel (co-investigator: A. [name]) to determine appropriate steps.

Potential subjects will be carefully screened before recruitment with respect to their medical history. This includes: history of head trauma, surgical aneurysm clips, cardiac pacemaker or any other type of implants, metal rods or plates. They will be queried about their previous surgeries, hearing aid, intrauterine devices, dentures and pregnancy. Individuals with any one of these contraindications will not be recruited for the study.

If there are any concerns about a subject in need of clinical attention, the PI will be made aware of the issue immediately and will consult with appropriate medical personnel (co-investigator [name]) to determine appropriate steps. The PI and medically trained co-investigators will assess the needs of the subject and offer the subject either prompt treatment or medical referral, whichever is

appropriate for the situation. There is a licensed clinician on site 40 hours per week, and other MGH resources can be used as necessary.

Potential Benefits

Participants may find that talking about marijuana use increases their awareness of any issues related to drug use. Any participant who asks about treatment will be provided information regarding local drug treatment programs.

Information developed from this study may help researchers in the future. Specifically it is expected that this study will provide valuable information about effects and consequences of MM use, where few studies have been published. The proposed project will fill a critical gap in the addiction literature, at a critical time when cannabis is being legalized for 'medical' use with little known about effects of MM on target symptoms, addictions, neurocognition or brain structure and function.

MONITORING AND QUALITY ASSURANCE

All participants will have contact information for the principal investigator and the study coordinator if they have questions at any time. [name] is responsible for the overall management of the study and will maintain regular communication with all of the study staff. The PI will meet weekly with all study investigators to review the details of data acquisition and analysis as well as any minor problems. In the event of any significant adverse event, the PI will be contacted immediately. The PI is responsible for the generation of summary reports to NIH documenting this process and outcome, which will also be included in the Continuing Review reports to the IRB.

Serious adverse events are not expected as a result of the study procedures. Should one occur, it will be reported by telephone or email by the principal investigator to the Partners IRB according to current PHRC Adverse Event Reporting Policy (version dated: March 13, 2007). All adverse events (if not serious) will be reported in writing to the Partner's Human Research Committee. All information regarding experimental subjects will be kept in the offices of the Principal Investigator. All data will be identified by a unique code number.

References

1. Substance Abuse and Mental Health Services Administration, Results from the 2013 National Survey on Drug Use and Health: Summary of National Findings, NSDUH Series H-48, HHS Publication No. (SMA) 14-4863. Rockville, MD: Substance Abuse and Mental Health Services Administration; 2014:31.
2. Substance Abuse and Mental Health Services Administration, Results from the 2013 National Survey on Drug Use and Health: Summary of National Findings, NSDUH Series H-48, HHS Publication No. (SMA) 14-4863. Rockville, MD: Substance Abuse and Mental Health Services Administration; 2014:25.

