Effect of Medical Marijuana on Neurocognition and Escalation of Use

NCT03224468

Date: 1/28/2022

PARTNERS HUMAN RESEARCH COMMITTEE

DETAILED PROTOCOL: Effect of Medical Marijuana on Neurocognition and Escalation of Use

Protocol #: 2015P001600

Principal Investigator: [name].

Co-Investigator: A. [name]

Summary of Changes Made and Rationale

The IRB protocol, attached, was written for a pilot phase of the trial, and was updated when we received the R01. All measures, outcome definitions, and sample size calculations were up to date in clinicaltrials.gov (NCT03224468). The statistical analysis section was amended before any data were analyzed except for the propensity score analysis for missing data, explained below. No changes were made after looking at the data, except for the propensity score analysis.

Method of randomization:

In Year 1 of the study, we realized that many participants, who were interested in obtaining an MMC never obtained one because of barriers such as expense or needing to go outside the usual healthcare system. We therefore changed our randomization from 1:1 to 2:1 MMC:WLC early in the trial in order to have enough participants in the MMC arm.

Outcomes and outcome definitions:

Outcome measures and definitions were updated on 07/19/2017 in clinicaltrials.gov (NCT03224468), but were not explicitly stated in the IRB protocol.

Primary Outcome Measures:

- Cannabis Use Disorder Symptoms (*Time Frame: Baseline to 12 Weeks*)
 - o The DSM-5 Cannabis Use Disorder Checklist will evaluate symptoms of CUD (number of symptoms).
- Changes in Symptoms of Depression and Anxiety (*Time Frame: Baseline to 12 Weeks*)
 - o For those with depression and anxiety symptoms, the Hospital Anxiety and Depression Scale will be used to assess symptoms.
- Changes in Pain (*Time Frame: Baseline to 12 Weeks*)
 - o For those with pain, the Brief Pain Inventory Severity Scale (BPI-S) will be used to assess levels of pain.
- Changes in Sleep (*Time Frame: Baseline to 12 Weeks*)
 - o For those with insomnia, the Athens Insomnia Scale will be used to assess symptoms.

Secondary Outcome Measures

- o General Medical/Psychiatric Health (*Time Frame: Baseline to 12 Weeks*) The Short Form-12 Health Survey (SF-12) will be used to assess self-report of emotional and physical functioning.
- Cognitive Testing (*Time Frame: Baseline to 12 Weeks*)
 - o Verbal learning/memory, attention, working memory, and complex decision-making will be assessed.

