- Brain-based Measures (*Time Frame: Baseline to 1 Year*)

- Changes in resting state functional connectivity and task-associated activation in brain regions involved in reward, inhibitory control, and working memory will be assessed.

The IRB protocol includes exploratory outcomes that were not presented in this manuscript, but will be included in future publications.

Statistical Analysis: The IRB protocol did not include the final statistical plan. When we brought [name], an experienced clinical trial statistician, on this project in Year 2 of the study, well before any analysis had been conducted, he suggested that instead of a random slopes analysis that assumes the effect of the drug will be to gradually increase the effect or outcome, ie a time x treatment interaction, he suggested we should assume a constant treatment effect over the follow up period, 2 weeks, 1 month, 3 months. [name] also advised us not to adjust for covariates as we originally proposed to do, but to only adjust for baseline symptoms, since randomization should have accounted for differences and we had no strong prior information about what covariates would have an important effect on CUD in people seeking cannabis for medical complaints. [name], without access to the data, made these recommendations to Drs [name] and [name] after which [name], who had access to the data, implemented the analyses.

Propensity score analysis for missing data: We could not ensure that participants in the MMC condition obtained an MMJ card, and we could not give participants a MMJ card because of state and hospitals regulations, a stated limitation of the study. Thus, we conducted a post hoc sensitivity analysis to verify the positive findings of the primary analysis in the final stages of the analysis when we realized that there was a problem with differential drop-out between the randomization and the baseline visit in the MMC and WLC groups.

Sample size calculation:

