Screening: Participants who have expressed interest in participating in the study will undergo a brief phone screen to assess eligibility. We plan to phone screen about 2000 participants. If they are eligible according to the phone screen, they will be scheduled for an in-person (or teleconference) study visit. At this visit, a consent form will be reviewed with the study staff. Participants who give permission to receive text messages from the study staff will receive appointment reminders via text two days before upcoming appointments. In addition, subjects will be instructed on how to use our phone app for tracking their medical marijuana use, they will fill out some questionnaires and also do a urine drug and if applicable, a pregnancy test. Also at this visit, participants will be randomized to either the active study group or the waitlist control group. We plan to randomize 200 participants to each group.

Study Design: The active study group will be asked to call the study staff once they receive their MM cards. A staff member will follow up via phone with participants who do not contact study staff within approximately two weeks after the screening visit. Staff will contact participants again after approximately four weeks and six weeks to check in on the status of the medical marijuana card application. If after six weeks, a participant still has not made any progress on the application for a

medical marijuana card (i.e., made an appointment with a doctor who recommends medical marijuana), the participant will be discontinued from the study and a three-month follow-up visit will be scheduled.

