Family history of Addiction	KSADS	x						
Provider Expectations for Recovery Scale	PERS	x						
Substance Use								
Frequency of substance use	TLFB (MJ, EtOH, tobacco, other drugs)	x	x	x	x	x	x	x

Cannabis Use Disorder Screen	DSM-5 Cannabis Use Disorder Checklist	x	x	x	x	x	x	x
MJ craving	MCQ-SF		x	x	x	x	x	x
Marijuana Motives	MMM					x		
Marijuana Withdrawal (if stop)	CWS		x	x		x	x	x
MJ use severity	CUDIT		x	x	x	x	x	x
Harmful drinking	AUDIT	x				x	x	x
Alcohol consumption urge	URGE		x	x	x	x	x	x
Expectancy of MMJ effects	MMEEQ	x	x		x	x	x	x
Reflection of MMJ effects (qualitative)							x	x
Symptoms								
Pain level	BPI	x	x	x	x	x	x	x
Pain Catastrophizing Scale	PCS	x	x	x	x	x	x	x
Perceived Stress Scale	PSS	x	x	x	x	x	x	x
Clinician's Severity Scale	CGI		x	x	x	x	x	x
Insomnia	AIS	x	x	x	x	x	x	x
Anxiety Scale	HADS	x	x	x	x	x	x	x
Delusions and Psychosis	PDI		x		x	x	x	x
Difficulties due to health conditions	WHODAS	x	x			x	x	x
Post-traumatic stress symptoms	PCL	x						x
COVID-19 Specific Questionnaires								
Remote Pre-Visit Form	PVF	x	x	x	x	x	x	x
Effects of COVID-19 pandemic on mood, pain, sleep, lifestyle	COVID Impact	x	x	x	x	x	x	x
Impact of epidemic/pandemic on various areas of life	EPII	x						
Changes in substance use since COVID-19 pandemic	Covid19-CSU	x						
Cognitive Testing								
Verbal learning/memory, attention, working memory, and complex decision-making	CANTAB		x		x	x	x	x
Intelligence / reading	WTAR	x						
MRI Scan								
MPRAGE	Structural		x					x
Resting state	Functional connectivity		x					x
Task-based (i.e. working memory, inhibitory control)	Task-based fMRI		x					x

Drug Testing: At all study visits, participants will provide a urine sample, which will be used to qualitatively screen for cannabis use as well as other substances of abuse. For participants who provide written consent for sample shipment, urine samples will be shipped to quantitatively screen for amount of THC metabolites in urine. Samples will only be shipped for participants who report recent marijuana use and/or qualitatively screen positive for THC. An alcohol reading may also be taken if there is any concern about a participant being intoxicated.

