Urine Collection During Remote Data Collection: While we must conduct remote study visits, participants will be asked to consent to shipping their urine samples to study staff for analysis of cannabinoid metabolites. Participants who do not consent to remote urine collection will not be penalized and will not receive materials for shipping their urine for testing. Participants who consent

will receive urine sample kits by mail prior to their remote visits. Kits include a sample cup, biohazard bag, packaging bag, UPS shipping bag, and detailed instructions on how to provide and package their urine sample. Participants will be instructed to leave the packaged sample at the location where their mail is picked up at their home before the scheduled pickup time. Because there is no staff at our MGH offices, study staff will schedule a UPS pickup for overnight shipping from the participant's home to the home of our Center Director, [name], MD, who will be available to transport urine samples to the -80 degree freezer in the Thier Building on the MGH campus for storage prior to batch transport to Colorado for analysis of cannabinoid metabolites central to understanding the primary outcomes of the study. [name] will pipette aliquots of samples into labeled vials for freezer storage. Samples will be batch shipped on dry ice to Colorado when that lab is again functioning at its capacity and able to conduct quantitative assay for cannabinoid metabolites per study protocol. [name] is approved as Emergency Level 4 Research Staff Essential Personnel, and as such has access to the -80 degree freezer in the Their Research building, as per guidance from hospital leadership. Drs. [name] and [name], and 2 other members of study staff also have this approval and can take over this urine aliquoting and transport task should [name] be unable to perform it due to illness or redeployment.

Online Dosing Diaries: All participants will be asked to keep a daily log of (1) marijuana use, and (2) ratings of pain, sleep quality, mood, and general health. They will be asked to send in data once per day during the first three months of study participation (from Visit 1 to Visit 5). We will collect this data using Secure Survey, a web application designed to collect data from a modern user group on their mobile, tablet, or desktop devices.

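### Allocation moved from 1:1 to 2:1 during the trial, which ties enrolment period to arm, but the final model adjusts only for baseline symptoms and has no allocation-phase term

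*Combined protocol and SAP*

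**What the plan says.** Under Method of randomization, the Summary of Changes explains the trigger: "In Year 1 of the study, we realized that many participants, who were interested in obtaining an MMC never obtained one". The team therefore "changed our randomization from 1:1 to 2:1 MMC:WLC early in the trial". It gives no date for the switch and no count of participants randomised under each ratio.

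Under Statistical Analysis, the same summary says the attached protocol does not contain the final plan, so this summary is the only statement of the final analysis. That analysis assumes a constant treatment effect over the 2-week, 1-month and 3-month visits. The covariate advice was to "only adjust for baseline symptoms, since randomization should have accounted for differences and we had no strong prior information about what covariates" would matter for CUD.

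The older Analytic Plan in the attached protocol names baseline marijuana use, primary disorder, age and gender as covariates of interest. Neither text mentions a term, stratum or sensitivity analysis for allocation phase or enrolment period. The post hoc propensity score analysis is described only for differential drop-out between randomisation and baseline.

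The attached protocol (version dated 04/15/2020) shows that study conditions changed over time. For those who pass the phone screen it says "they will be scheduled for an in-person (or teleconference) study visit". The urine-collection text begins "While we must conduct remote study visits". The measures table includes a questionnaire on "Effects of COVID-19 pandemic on mood, pain, sleep, lifestyle".

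**The concern.** When the ratio changes, the probability of assignment to MMC depends on when a person enrolled. Early enrolees had a 1/2 chance of WLC and later ones a 1/3 chance, so the pooled WLC arm contains proportionally more early enrolees. This is systematic, not chance imbalance, and it holds for any split with people in both phases.

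Neither reason given for the sparse model covers this. That randomisation accounts for differences is true within a phase but not across pooled phases. The lack of prior information concerns prognostic covariates for CUD. Allocation phase is a design variable, needed because it determines the assignment probability.

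At stake is a bias in every between-arm estimate equal to the phase imbalance times the residual outcome difference between phases. If later enrolees report more CUD symptoms at follow-up, the MMC effect on CUD is overstated; if fewer, it is understated.

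**Working it through.** **Nearest stated figure.** The plan gives no number on this point. The closest is 85% power for CUD at N=200, two-sided 0.05, for 20% versus 5% (mean symptoms 0.4 versus 0.1). For two proportions with continuity correction, 85% power needs 99 per arm, so the figure reproduces. Without the correction, a 67:133 split gives 84.9%. No SD is stated for the symptom count. Solving for it from 85% power with 100 per arm gives 0.3 × √50 / (1.960 + 1.036) = 0.708. This is an assumption, used only to express results in symptoms.

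**Inputs.**
- From the Summary of Changes: the two ratios; N=200 in total; about 33 per group, so 66, in each symptom subgroup.
- Assumed: fraction f randomised at 1:1 of 5%, 10%, 20% or 30%; drift between phases, left after baseline adjustment, of 0 to 0.5 SD.

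Sections V and VI of the protocol speak of 200 per group and 400 enrolled. At that size the bias below would be the same and the error rates higher.

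**Phase share by arm.** P(MMC) = 0.5f + (2/3)(1−f). Early share in MMC = 0.5f / P(MMC). Early share in WLC = 0.5f / (1−P(MMC)).

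For f = 0.30: P(MMC) = 0.15 + 0.4667 = 0.6167. The shares are 0.15/0.6167 = 24.3% and 0.15/0.3833 = 39.1%, a gap of 0.148.

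**Bias and false-positive rate.** Bias = gap × drift. SE = √(1/n1 + 1/n2) in SD units. Rate = P(|Z + bias/SE| > 1.96).

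For f = 0.30, drift 0.5, N=200: bias = 0.148 × 0.5 = 0.074; SE = √(1/123.3 + 1/76.7) = 0.145; bias/SE = 0.51; rate = 8.0%.

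| f at 1:1 | Early share MMC / WLC | Gap | Bias at 0.5 SD | Rate, N=200 | Rate, N=66 | SE increase with phase term |
|---|---|---|---|---|---|---|
| 5% | 3.8% / 7.3% | 0.035 | 0.018 SD | 5.16% | 5.05% | 0.29% |
| 10% | 7.7% / 14.3% | 0.066 | 0.033 SD | 5.57% | 5.19% | 0.55% |
| 20% | 15.8% / 27.3% | 0.115 | 0.057 SD | 6.77% | 5.58% | 0.97% |
| 30% | 24.3% / 39.1% | 0.148 | 0.074 SD | 8.02% | 5.99% | 1.26% |

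With zero drift the rate is 5.0% throughout. With f = 10% and 0.2 SD drift at N=200, the bias is 0.013 SD and the rate 5.1%.

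The last column is 1/√(1−r²) − 1, where r² is the squared correlation of arm with phase: 0.0059, 0.0110, 0.0191 and 0.0247.

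**Simulation.** The formula ignores that unmodelled drift also widens the estimated SE. A least-squares simulation (400,000 replicates, no treatment effect, 0.5 SD drift) gives milder rates without the phase term. At N=200 they are 4.99%, 5.24%, 6.27% and 7.14% for f = 5%, 10%, 20% and 30%. At N=66 and f = 30% the rate is 5.40%. With the phase term all rates lie between 4.93% and 5.03%, and the mean bias is within 0.0002 SD of zero.

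**In CUD symptoms (SD 0.708, N=200).** A 0.3-symptom difference between phases gives a bias of 0.020, 0.034 and 0.044 symptoms for f = 10%, 20% and 30%. That is 7%, 11% and 15% of the planned 0.3-symptom effect, with rates of 5.4%, 6.2% and 7.1%. A 0.1-symptom difference gives a bias of 0.007 to 0.015 and rates of 5.0% to 5.2%.

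**The case against.** The strongest reply is that no harm is shown. Both f and the drift are assumed. A change made early suggests a small f, and at f = 5% or 10% the simulated error rate hardly moves even at the largest drift. On the back-solved SD, 0.5 SD is about 0.35 symptoms. That exceeds the whole planned treatment effect (0.3) and is more than three times the expected WLC mean (0.1), and it would have to survive adjustment for each person's own baseline. This stands, and it is why the point is minor.

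The pandemic evidence is also weak. Because the switch came early, anyone enrolled under the remote procedures was presumably randomised at 2:1. A shift inside that phase matters only by moving its average. The COVID-19 items show that conditions changed, not that baseline-adjusted outcomes drifted. This stands too.

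Two further limits hold. Pooling is inferred from the absence of any separate or stratified analysis, though it is the natural reading. The shares describe randomised participants, and uneven drop-out by phase would alter them among those analysed. That changes the illustrative figures, not the argument.

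What the reply does not rescue is the stated rationale. Randomisation under two ratios does not balance anything related to enrolment phase in the pooled sample, and the documents give a reader no means of bounding the effect.

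**Conclusion.** The concern holds and is minor. The association between arm and enrolment phase follows from the change of ratio alone and needs no assumption beyond both phases being analysed together. Its consequence depends on two quantities the documents do not give: the fraction randomised at 1:1 and any drift left after baseline adjustment. Over the ranges used, the bias is probably small and may be nil. The worst false-positive rate at N=200 is 8.0% by formula and 7.1% by simulation. In a 66-person subgroup the corresponding figures are 6.0% and 5.4%. Confidence in the practical importance is medium at most. The case for acting is that one model term removes the dependence on an unstated assumption of no phase difference.

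**What to change.** Include allocation phase (1:1 versus 2:1) as a fixed factor beside the baseline score in the between-arm models. Report the date of the switch and the numbers randomised to each arm in each phase. Because the document describes analyses already done, present the phase-adjusted result as a sensitivity analysis labelled as added after the data were analysed, as the team did for its propensity score analysis.

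The cost is one model degree of freedom, a standard error 0.3% to 1.3% larger if 5% to 30% were randomised at 1:1, and a table of four counts. For CUD at N=200 and SD 0.708, power falls by about one point or less: 81.6% to 81.1% at f = 10%, and 83.0% to 82.1% at f = 30%. In a subgroup of 66 with f = 5%, the phase effect would rest on about three people (0.05 × 66 = 3.3), so there the counts will be more informative than the adjusted estimate.
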